**Statement of Compliance**

This document is a protocol for a research project. This study will be conducted in compliance with all stipulation of this protocol, the conditions of the ethics committee approval, the NHMRC National Statement on ethical Conduct in Human Research (2007) and the Note for Guidance on Good Clinical Practice (CPMP/ICH-135/95).

## 2. STUDY SYNOPSIS

Provide brief information

Title:	Hidradenitis suppurativa treated with follicular unit excision: A prospective controlled pilot study
Short Title:	Hidradenitis suppurativa treated with follicular unit excision: A prospective controlled study
Design:	Open-label, interventional
Study Centres:	Sinclair Dermatology, Melbourne Australia
Hospital:	
Study Question:	How effective is follicular unit excision for the treatment of mild-moderate hidradenitis suppurativa?
Study Objectives:	
Primary Objectives:	The study's primary objective is to determine change in several hidradenitis suppurativa assessment scores score throughout follow-up visits in the first 24 weeks after follicular unit excision
Secondary Objectives	
 
i) To compare the changes in Hidradenitis Suppurativa assessment scores between intervention and control groups up to 24 weeks and on the treated sites before and after follicular unit extraction
 
ii) To compare the number of disease flares between the treated and control groups for 24 weeks after treatment
 
iii) To determine if specimens contain hair follicles, sebaceous glands, apocrine glands and eccrine glands on histopathology
 

Key Inclusion Criteria:	
 
i) Patients aged <math>\geq 18</math> years with hidradenitis suppurativa
 
ii) Mild-moderate hidradenitis suppurativa defined by Hurley stage 1 up to 2A
 
iii) Minimum diagnosis of 3 months prior to baseline
 
iv) Active hidradenitis suppurativa present for <math>\geq 3</math> months from initial diagnosis
 

Key Exclusion Criteria:	
 
i) Current treatment with systemic antibiotics, retinoids, immunosuppressants or biologic agents at discretion of the investigator
 
ii) Extensive scarring
 
iii) Absence of terminal hairs in target areas
 
iv) Previous laser hair removal in target areas
 
v) Pregnant or lactating women
 

Number of Planned Participants :	24
Investigational procedure:	Follicular unit excision using 0.8 mm Ertip® punch
Data analysis	The primary objective is to evaluate the efficacy of follicular unit excision in the treatment of adults with mild to moderate hidradenitis suppurativa. The primary analysis will be conducted to assess the primary and secondary endpoints once all participants have completed the Week 24 visit.
Safety considerations:	
Statistical Methods:	Paired t test to assess change in Hurley stage, Hidradenitis Suppurative-Physician's Global assessment score, numerical pain score, IHS4 score, HiSCR score.
Subgroups:	

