## 6. STUDY OBJECTIVES

### 6.1 HYPOTHESIS

Participants receiving FUE will have lower scores for HiSCR, HS-PGA, IHS4, NRS30 compared to those receiving standard topical resorcinol/clindamycin.

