#### Primary objective.

1. To evaluate the effectiveness of FUE in reducing severity score of mild to moderate HS.

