#### Secondary objective.

2. Comparing scores of HS severity assessments between intervention and control group at week 6, 12 and 24 after follicular unit extraction.
3. Comparing scores of HS severity assessments before and after follicular unit extraction on the treated site at week 6, 12 and 24 after follicular unit extraction.
4. To compare the number of disease flares between intervention and control group over 24 weeks.
5. To determine if specimens contain HFs, sebaceous glands, apocrine glands and eccrine glands on histopathology.

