## 9.3 STATISTICAL METHODS TO BE UNDERTAKEN

Abscess and nodule counts will be recorded and then compared at the study visits up to week 24. This will be done using the paired t test.

Paired t test will also be used to compare changes in HS-PGA, IHS4 and HiSCR scores between the treated and control sites.

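### The primary objective reads as before/after change in several unnamed scores, while the randomised comparison that the hypothesis rests on is only secondary

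*Protocol*

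**What the plan says.** **Primary objective.** Section 2 (Study Synopsis) sets out to "determine change in several hidradenitis suppurativa assessment scores score throughout follow-up visits in the first 24 weeks after follicular unit excision". Section 6.2 words it as "To evaluate the effectiveness of FUE in reducing severity score of mild to moderate HS". Neither mentions the control group, and neither picks a score or a visit.

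**Hypothesis.** Section 6.1 has one hypothesis, and it is between arms: "Participants receiving FUE will have lower scores for HiSCR, HS-PGA, IHS4, NRS30 compared to those receiving standard topical resorcinol/clindamycin".

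**Secondary objectives.** The synopsis places here "To compare the changes in Hidradenitis Suppurativa assessment scores between intervention and control groups up to 24 weeks", joined in the same item to a before/after comparison on the treated sites. Section 6.2 lists the two separately: "Comparing scores of HS severity assessments between intervention and control group at week 6, 12 and 24 after follicular unit extraction", and then "Comparing scores of HS severity assessments before and after follicular unit extraction on the treated site at week 6, 12 and 24".

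**Analysis.** The synopsis names a paired t "test to assess change in Hurley stage, Hidradenitis Suppurative-Physician's Global assessment score, numerical pain score, IHS4 score, HiSCR score", which is five scores. Section 9.3 adds: "Paired t test will also be used to compare changes in HS-PGA, IHS4 and HiSCR scores between the treated and control sites". Section 6.4.1.8 puts assessments at Weeks 0, 6, 12 and 24, so there are three post-baseline visits. The Data analysis row of the synopsis describes the primary objective as an evaluation of efficacy and refers to primary and secondary endpoints, but no section says which measure is the primary endpoint.

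**The concern.** A randomised control arm lets a trial separate what the procedure does from what would have happened anyway. Here that arm serves a secondary objective, while the objective that carries the efficacy claim is worded as change after FUE.

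The protocol itself supplies other reasons for scores to move:

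- Entry requires active disease in a condition that flares and recedes (sections 5.2, 5.3 and 7.2), which invites regression to the mean.
- Section 6.4.1.6 allows medication, intralesional corticosteroids and surgical management of flares. Section 8.1 allows other anti-inflammatory medication.
- Investigators and participants know the allocation (section 6.6), and the principal investigator is one of the scorers (section 6.7).

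Followed as worded, the primary analysis would count improvement shared by both arms as efficacy. Because no score or visit is chosen in advance, the headline could also be picked from many results after the data are seen.

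**Working it through.** The protocol gives no alpha, effect size, SD or power, so there is no figure of its own to reproduce. What follows shows the consequence of the wording. Two-sided alpha of 0.05, normally distributed changes, and the drifts and correlations below are assumptions.

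**Inputs from the protocol.** 12 per arm (9.2); 20% loss to follow-up (9.1); five scores (synopsis, Statistical Methods); three post-baseline visits (6.4.1.8).

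**1. Before/after test when FUE has no effect.** Suppose both arms improve by d SD of the change score for reasons unrelated to FUE. The paired test in the FUE arm has 11 degrees of freedom, critical value 2.201 and noncentrality d × √12. The chance of a significant improvement is:

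| Shared drift d (assumed) | d × √12 | Before/after test significant | Between-arm test significant |
|---|---|---|---|
| 0.3 SD | 1.04 | 16% | about 5% |
| 0.5 SD | 1.73 | 35% | about 5% |
| 0.8 SD | 2.77 | 71% | about 5% |
| 1.0 SD | 3.46 | 88% | about 5% |

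The between-arm rate does not depend on d, because a drift common to both arms cancels in the difference. Simulation at drifts of 0.5, 0.8 and 1.0 SD gave 4.9% to 5.1%.

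**2. No score or visit chosen.** Five scores × three visits = 15 possible tests. This step concerns between-arm tests under no effect, not the before/after contrast in step 1.

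- Independent tests, either direction: 1 − 0.95^15 = 54%.
- Independent tests, at least one in favour of FUE: 1 − 0.975^15 = 32%.
- Correlated tests, by simulation of 20,000 null trials with 12 per arm:

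| Correlation between scores / between visits (assumed) | Any false positive | At least one favouring FUE |
|---|---|---|
| 0.5 / 0.5 | 42% | 22% |
| 0.6 / 0.6 | 36% | 19% |
| 0.7 / 0.6 | 34% | 17% |

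Repeat runs differ by about one percentage point, so the ranges are about 33–42% and 17–22%.

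**3. What a between-arm primary could detect.** The two-sample t test with 12 per arm has 22 degrees of freedom, critical value 2.074 and noncentrality d / √(1/12 + 1/12) = 2.449 × d. Power of 80% needs d of about 1.20 SD. With 20% loss (12 × 0.8 = 9.6, taken as 10 per arm) it needs about 1.32 SD. At d = 0.8 SD, power is 47% with 12 per arm and 40% with 10.

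**The case against.** **The single-arm reading is an inference.** Section 6.2 is silent on the comparator rather than explicitly single-arm, the title calls the study controlled, and the before/after contrast has its own place among the secondary objectives. This stands: a reader might infer that the protocol firmly fixes an uncontrolled primary analysis, and the documents do not go that far. But if the primary objective can be read either way, it still has to be settled, and the explicit between-arm comparison is secondary in both places.

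**It is a pilot.** The pilot label excuses the lack of a power calculation. It does not excuse the order of the objectives, because the synopsis and section 6.2 speak of efficacy and effectiveness.

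**The count of 15 is soft.** This also stands. Hurley stage is not among the outcome measures in 6.3, and 6.4.1.8 calls for it at baseline. HiSCR is a yes/no response already defined against baseline. HS-PGA, IHS4 and HiSCR share the same lesion counts, so correlations may be higher than assumed and the rates lower.

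**Co-treatment can work the other way.** Medication given to stabilise disease before FUE could lower Week 0 scores and so shrink the before/after change. This is fair: the bias has no certain direction, but the before/after contrast cannot remove it.

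**Between-arm results will exist anyway.** True: the secondary objective yields them at Weeks 6, 12 and 24. What is missing is the advance choice of one, which matters because sections 9.1 and 9.2 want the results to size later studies.

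**Conclusion.** The point holds. The primary objective does not clearly use the randomised control arm, it names no score or visit, and it overlaps with a secondary objective. The objectives and their order are set in the protocol, so a later analysis plan could not reverse them without contradicting it.

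The size depends on drift that the documents do not quantify. Two stronger conclusions are tempting and are not supported:

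- That a positive primary result is likely even if FUE does nothing. At 0.5 SD drift the rate is 35%; among the drifts shown it passes one half only at 0.8 SD and above.
- That some score or visit will usually favour FUE by chance. Under the assumed correlations this happens in 17–22% of null trials, and in 32% even with independent tests.

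**What to change.** Make the primary objective the between-arm difference, as randomised, on one named score at one named visit, reported with a 95% confidence interval. IHS4 at Week 24 adjusted for Week 0 IHS4 is one reasonable choice: the appendix defines it and it can be computed from lesion counts at every visit. The essential step is to name one score and one visit.

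Label the other scores, visits and flare counts secondary and descriptive, and change within the FUE arm supportive only. Remove the duplication between the primary and secondary objectives.

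Align sections 2, 6.1, 6.2 and 9.3. In 9.3, replace the paired t test for treated versus control with an independent-groups or baseline-adjusted analysis, since the arms are different people.

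The cost is a protocol amendment in wording only, best made before any outcome data are analysed. The price is a wider and probably less favourable headline estimate, with only differences of about 1.2 SD detectable at 80% power with 12 per arm. Unblinded scoring remains a limitation that this change does not cure.

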### 3. GLOSSARY OF ABBREVIATIONS & TERMS

Abbreviation	Description (using lay language)
HS	Hidradenitis suppurativa
HF	Hair follicle
FUE	Follicular unit excision
IHS4	International Hidradenitis Suppurativa Severity Score System
Hi-SCR	Hidradenitis Suppurativa Clinical Response
HREC	Human Research Ethics Committee
HS-PGA	Hidradenitis Suppurativa Physician Global Assessment
ICH GCP	International Council for Harmonisation of Technical Requirements for Pharmaceuticals for Human Use Guideline for Good Clinical Practice
Nd:YAG	Neodymium-doped yttrium aluminum garnet
SAE	Serious adverse event

## 5. INTRODUCTION/BACKGROUND INFORMATION

### 5.1 LAY SUMMARY

This study is looking at follicular unit extraction to treat hidradenitis suppurativa, a condition that causes inflammation of hair follicles resulting in severe pain and scarring. Follicular unit extraction is a technique used in hair transplants to entirely remove hair follicles. We want to test whether or not by removing hair follicles using hair follicle extraction technique reduces inflammation and improve the quality of patients' life. We will do hair follicle extraction on both sides of either the armpit or groin and compare it with topical routine treatments to assess whether or not there is improvement. We will follow the participants until week 24 of the study.

### 5.2 INTRODUCTION

Hidradenitis suppurativa (HS) is a chronic skin disease which predominantly affects the skin of intertriginous areas through an inflammatory process and results in recurrent nodules, abscesses, sinuses, fistulas, and scarring. Based on a limited number of smaller studies, the estimated lifetime risk is 1%, with 30% having moderate-to-severe disease. HS develops at an average age of 22 years and persists for an average of 19 years. Genetic factors appear to play an important role in HS, given that up to 42% of patients report a family history of the condition. HS has a severe emotional and psychosocial effect on sufferers, which includes a negative impact on their ability to function socially.

### 5.3 BACKGROUND INFORMATION

HS was once considered a disease of the apocrine gland, but newer evidence firmly implicates direct follicular involvement in disease pathogenesis. Over 95% of early lesions (< 3 days old) include

hyperkeratosis, occlusion of the follicular unit and an associated perifolliculitis. These are often accompanied by dilatation of the hair follicle (HF) and subsequent stasis in both the apocrine and eccrine glands. While apocrine stasis, hyperplasia and a periglandular inflammatory infiltrate are observed in and around the apocrine glands in 33–90% of cases of HS, they are universally accompanied by extensive inflammation of the HF, eccrine gland and cystic structures, and are thought to be a secondary phenomenon. It has recently been observed that there is a thinning of the basement membrane zone around the junction between the HF and sebaceous gland in HS skin. This area of weakness may predispose to rupture of the hair follicle and spillage of its contents into the dermis and a subsequent inflammatory response. Furthermore, the identification of free keratin filaments in the dermis supports that mechanism and is consistent with follicular rupture playing a key role in disease pathogenesis.

The management of HS is currently multifactorial. Lifestyle changes e.g., smoking cessation and weight loss can reduce the frequency of HS flares. Other lifestyle modifications such as wearing loose clothing may reduce the severity of flares. Systemic therapy includes antibiotics, hormonal therapy e.g. spironolactone, retinoids and immunosuppressants. However, the disease often recurs following therapy interruption or discontinuation. The tumour necrosis factor- $\alpha$  inhibitor adalimumab is a relatively effective treatment, with 41.8-58.9% of adult patients achieving satisfactory clinical response. In chronic refractory cases, surgery, including deroofing and incision and drainage or ablative lasers may be used. Therefore, early intervention is critical to prevent progression of disease to a disfiguring recalcitrant stage.

Follicular unit excision (FUE) is a minimally invasive surgical technique used in hair transplantation surgery where hair grafts are extracted from the donor area and implanted in the recipient area under local anaesthesia. Although grafts are usually harvested from the back and sides of the scalp, other donor sites include the beard, chest and other parts of the body. In FUE, the skin around a follicular unit is scored using a 0.8-1 mm circular punch mounted on a motorized hand device, and the graft is subsequently extracted. The extraction leaves a wound which heals by secondary intention. Residual scars are pin-point dots which are virtually imperceptible to the naked eye.

Although FUE is mostly used in hair transplantation, it has been used for other dermatological indications. Notably, extraction of pigmented hair grafts and placement into depigmented skin in patients with stable vitiligo resulted in skin re-pigmentation. This is likely due to migration of follicular melanocytes to vitiliginous skin.

Laser hair removal has been shown to be effective in reducing flares and severity of HS. In addition, deroofing with carbon dioxide laser with hair follicle removal using a neodymium-doped yttrium aluminum garnet (Nd:YAG) laser has been shown to reduce recurrence rates. Even in mild HS, Nd:YAG laser hair depilation increased patient satisfaction and reduced mean HS severity score.

To our knowledge, FUE to treat HS has not been attempted. Apocrine and eccrine glands are known to reside next to HFs. Given that HFs and/or apocrine glands are central to the pathophysiology of HS, and that laser hair removal has been shown to be an effective treatment, we propose that FUE can be an effective treatment modality for HS. In contrast to laser hair removal, FUE would also remove apocrine glands. In addition, hair removal using laser is often temporary, with hair regrowth occurring within a few months if laser treatment is not maintained. On the other hand, FUE would result in permanent removal of HFs and associated apocrine glands, thereby offering a more long-lasting solution.

## 6. STUDY OBJECTIVES

### 6.1 HYPOTHESIS

Participants receiving FUE will have lower scores for HiSCR, HS-PGA, IHS4, NRS30 compared to those receiving standard topical resorcinol/clindamycin.

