## 9.2 POWER CALCULATIONS

This pilot study uses 12 participants in each group (intervention vs controlled) and results from this will allow us to calculate the sample size required for statistical power in future clinical studies.

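### The between-arm outcome is the score at each visit in sections 6.1 and 6.2 but the change in score in the synopsis and section 9.3, and nothing says which governs

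*Protocol*

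**What the plan says.** Four places in the Protocol define the comparison of FUE with control.

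- **6.1 Hypothesis** (level): "Participants receiving FUE will have lower scores for HiSCR, HS-PGA, IHS4, NRS30 compared to those receiving standard topical resorcinol/clindamycin". No visit is named.
- **6.2, objective 2** (level, at each visit): "Comparing scores of HS severity assessments between intervention and control group at week 6, 12 and 24 after follicular unit extraction". The before-and-after comparison on treated sites is listed separately as objective 3.
- **2 Synopsis, secondary objective i** (change): "To compare the changes in Hidradenitis Suppurativa assessment scores between intervention and control groups up to 24 weeks". The synopsis method line also refers to change, through a paired t "test to assess change in Hurley stage" and other measures that include pain.
- **9.3 Statistical methods** (change): "Paired t test will also be used to compare changes in HS-PGA, IHS4 and HiSCR scores between the treated and control sites". Pain is not in this list. Abscess and nodule counts are to be compared at the visits, without saying whether as level or change.

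No section says which version takes precedence. Scores are taken at weeks 0, 6, 12 and 24 (6.4.1.8), and also at screening (6.4.2.1, Appendix 2).

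**The concern.** A comparison of levels and a comparison of changes are different estimates from the same data, and in a small trial they can be well apart. Both are written into the Protocol as the between-arm comparison, so either could be reported afterwards as the planned result. The trial is open-label and the principal investigator is one of the scorers (6.6, 6.7), so leaving that choice open until the data are seen is an avoidable weakness.

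It also affects the stated purpose of the pilot, which is to supply figures for sizing later studies (9.1, 9.2). The SD to carry forward is not the same for a score, a change and a baseline-adjusted score.

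The point is separate from the use of a paired test on two independent groups. It would remain after an independent-samples test was substituted.

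**Working it through.** **The plan's own figure.** Section 9.2 states "This pilot study uses 12 participants in each group (intervention vs controlled"), and 12 + 12 = 24 agrees with 9.1. No alpha, power, effect size or SD is given, so there is nothing further to reproduce. Section 6.4.1.1 gives a total of 20 instead, or 10 per arm. Randomisation is 1:1 with no stratification factor named (6.6).

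**Step 1: how the two estimates differ.** Write Y for the mean follow-up score, B for the mean baseline score, and F and C for the arms. With complete data:

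(Y_F − Y_C) − [(Y_F − B_F) − (Y_C − B_C)] = B_F − B_C

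The gap is exactly the between-arm difference at baseline. This is algebra and needs no assumption.

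**Step 2: size of that difference.**

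- 12 per arm: SD = √(2/12) = 0.41 baseline SDs; 95% range ±1.96 × 0.408 = ±0.80. The chance of exceeding 0.5 SD is 2[1 − Φ(0.5/0.408)] = 22%.
- 10 per arm (the 6.4.1.1 total, or roughly what 20% loss leaves, 24 × 0.8 = 19.2): SD = √(2/10) = 0.45; the chance of exceeding 0.5 SD is 26%.

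The probabilities use a normal approximation.

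**Step 3: precision.** Let ρ be the baseline to follow-up correlation, with equal SD σ at both times. The variances of the three contrasts, in units of 2σ²/n, are 1 for the score, 2(1 − ρ) for the change and 1 − ρ² for ANCOVA:

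| ρ | score | change | ANCOVA |
|---|---|---|---|
| 0.3 | 1.00 | 1.40 | 0.91 |
| 0.5 | 1.00 | 1.00 | 0.75 |
| 0.7 | 1.00 | 0.60 | 0.51 |

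Which unadjusted version is more precise depends on ρ, which the Protocol does not give. ANCOVA has the smallest variance in each row.

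**Step 4: how often the conclusions differ.** Simulation with 12 per arm, normal scores, equal SDs, two-sample t tests at two-sided 0.05, and 40,000 trials per setting. The effect sizes and correlations are assumptions. The table gives the percentage of trials in which one test is significant and the other is not.

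| True effect | ρ = 0.3 | ρ = 0.5 | ρ = 0.7 |
|---|---|---|---|
| 0 | 8 | 8 | 9 |
| 0.5 SD | 21 | 25 | 32 |
| 0.8 SD | 31 | 34 | 41 |
| 1.0 SD | 32 | 32 | 33 |
| 1.5 SD | 15 | 9 | 6 |

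- With no effect, at least one of the two tests is significant in about 9% of trials, against 5% for a single test.
- Both significant in opposite directions: at most about 0.01% in any setting.
- Mean estimates agree in every setting, so neither contrast is biased.
- Power at 1 SD for ρ = 0.3/0.5/0.7: score 65/65/65%, change 51/65/86%, ANCOVA 67/75/89%.

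**The case against.** The strongest reply is that the text leans towards change. The synopsis primary objective, its secondary objective i, its method line and 9.3 all speak of change, so the wording in 6.1 and 6.2 could be shorthand. That does not settle it. Section 6.2 gives the before-and-after comparison its own item, which supports reading objective 2 literally as levels between arms, and no section ranks the two versions.

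A second reply is that covariate adjustment is commonly left to an SAP, which is not at hand here. That stands. An unadjusted comparison of change is valid under randomisation, and the absence of baseline adjustment is not itself an error in the Protocol. ANCOVA is offered because it removes the conflict. The fault is that the objectives disagree, and an SAP could follow one version only by departing from the other.

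Third, the disagreement rates are sensitive to the assumptions. They are highest at middling effects and fall quickly for large ones. Normality is doubtful for HS-PGA, a six-level ordinal scale, and for IHS4, a weighted lesion count in mild to moderate disease. The rates are therefore indicative only.

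A reader might infer that the two versions could show FUE significantly better on one and significantly worse on the other, or that one is biased. Neither follows: both have the same expected value, and opposite significant results practically never occur. A reader might also extend the point to HiSCR, which 6.1 and 9.3 both list. It does not extend: 6.4.1.8 defines HiSCR as a response relative to baseline, so the identity in step 1 does not apply.

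**Conclusion.** The inconsistency is real, lies in current text and should be corrected. It covers IHS4, HS-PGA and lesion counts. It covers pain only through the synopsis, because 9.3 omits pain. It does not cover HiSCR.

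The identity and the factor √(2/12) = 0.41 follow from the design. The disagreement rates, the 9% figure and the power values rest on assumed normality, equal SDs and, apart from the no-effect figure, assumed effects; all use correlations of 0.3 to 0.7. The 9% also applies only if the favourable version is chosen after the data are seen, and the Protocol does not suggest that anyone intends this. The consequence is an open choice between two legitimate results and some lost precision. In a 24-person pilot it is a moderate fault that is cheap to remove.

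**What to change.** In the synopsis, 6.1, 6.2 and 9.3, state one between-arm contrast for IHS4, HS-PGA, pain and lesion counts: the FUE minus control difference in the score at the visit, adjusted by ANCOVA for the participant's own baseline score. The treatment effect is then the same whether score or change is entered as the outcome, so the conflict disappears. Treat HiSCR separately as a responder outcome.

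Three details need stating with it:

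- **Which baseline.** Section 6.4.2.1 labels the screening scores as baseline, and 6.4.2.2 allows up to 28 days before Week 0. Define baseline as the last score recorded before the procedure, or before the start of topical treatment in controls.
- **Order at Week 0.** Section 6.4.2.2 lists FUE ahead of the severity scoring. State that scoring comes first.
- **Main time point.** Section 6.2 gives weeks 6, 12 and 24 equal standing. Name one; Week 24 fits the analysis timing in the synopsis.

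The cost is wording in four places, plus the baseline and scoring-order statements, and one degree of freedom. No extra visits, data or participants are needed. The 9.3 sentence can be corrected for the paired test in the same edit.
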